Women's First Gastrointestinal Activation Post-elective Cesarean Birth During Post-partum Hospitalization: A Comparison of Paula Method (the Circular Exercises Method) to Standard Care

NCT03761147

Document Date: August 7, 2017

Protocol

Caesarean section births constitute a significant percentage of all births in the western world and since the 1980s, there has been a constant rise. Caesarean section births can be associated with various post-operative complications, including poor peristalsis. In the hospital where this study was performed, the main treatment to accelerate post-operative bowel movement include early water drinking, early ambulation, and the use of laxatives. In this study these modalities are defined as the standard therapy.

Since the standard methods are not always effective and not suitable for all women who underwent a Caesarean delivery, there is a need for finding alternative treatments to accelerate bowel function. The method examined in this study is called "the Paula method for the training of ring muscles". According to this method, the contracting and releasing of the one ring muscle causes other involuntary ring muscles to be activated as well, including intestinal system muscles.

The purpose of this study is to examine the effectiveness of the Paula Method compared with the standard treatment offered to women after elective Caesarean delivery. In our study, gastrointestinal activation was defined as the initial appearance of intestinal sounds, first flatus passage and first defecation after the surgery.

This is randomized controlled clinical study examined the effectiveness of performing training according to the "Paula Method" to accelerate gastrointestinal activity in women after elective Caesarean section, compared with the standard treatment. The study included 64 women following elective Caesarean section

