performed under regional anesthesia. The participants were randomized on a 1:1 basis into a training group and a control group after signing the informed consent document. The women in the training group performed ring muscle training according to the Paula Method five minutes of exercise six times a day and those in the control group were treated with the standard protocol. During the experiment, data was collected on the timing of appearing the first bowel sounds, first flatus passage and first defecation after surgery. In addition, demographic data as well information regarding pain medications used during the hospitalization and course of the admission were collected.

All data collected during the study were analyzed using SPSS software. With the help of the software, an analysis of the demographics and health of the sample was performed. In addition, the mean time and standard deviations of first bowel sounds, first flatus passage and first defecation after surgery were obtained from the analysis, as well as frequency of postoperative complications in each group and other data. Based on these data, conclusions were drawn about the efficacy of the two intervention methods studied in this study in the operation of the gastrointestinal tract after cesarean section. The effect of taking different types of pain medication on the duration of hospitalization in both groups was examined using the Pearson correlation and the results were confirmed by T-test.

References

doi:10.1185/03007995.2015.1005833

Garbourg, P. (1992). Self healing: The secret of the ring muscles. Peleg Publishers & Balaban Publishers, p. 17.

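### Stay is correlated with each pain-medication type separately, with no joint test, arm term or between-arm test, so chance findings and one-arm results could be over-read

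*Combined protocol and SAP*

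**What the plan says.** The combined document has one unnumbered Protocol section. The last sentence of its data-analysis paragraph, just before the References, reads: "The effect of taking different types of pain medication on the duration of hospitalization in both groups was examined using the Pearson correlation". It continues: "the results were confirmed by T-test". This is the only analysis for which an inferential method is named. The rest of the paragraph mentions software, means, standard deviations and frequencies.

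The design text gives the size and allocation: "The study included 64 women following elective Caesarean section" and "The participants were randomized on a 1:1 basis into a training group and a control group". On exposure it says only that "information regarding pain medications used during the hospitalization and course of the admission were collected".

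The document does not give the number or list of medication types, how use is coded, a significance level, a multiplicity rule, a joint model, a term for arm, or a test that the association differs between arms. It does not say whether the correlations are run within each arm or in the pooled sample, and it does not call the analysis exploratory.

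**The concern.** Correlating stay with one medication type at a time gives a family of unadjusted tests whose size cannot be read from the plan. Either reading of the grouping leaves a gap.

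- **By arm** (the more natural reading): each type is tested twice and nothing compares the two results. A correlation that is significant in one arm and not in the other is not evidence that the arms differ.
- **Pooled**: there are half as many tests, but the randomised arm is left out of the analysis.

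On both readings, if types are used together (an assumption; the document is silent), the correlation for one type partly reflects the others. The plan nevertheless describes the result as an effect and treats a t-test as confirming it. At stake is a statement that a given pain medication lengthens or shortens stay, or does so in one group only, which a reader could take up in its own right.

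**Working it through.** The plan states no error rate, power or effect size, so it has no figure to reproduce.

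**Inputs.** N = 64 and 1:1 allocation are from the Protocol section. About 32 per arm is derived (64 / 2). Assumed: 5% two-sided per test, no adjustment, k = 2 to 6 medication types.

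**1. Chance of at least one false positive.** With m independent tests this is 1 − 0.95^m, where m = 2k by arm and m = k pooled.

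| k | by arm | pooled |
|---|---|---|
| 2 | 1 − 0.95^4 = 18.5% | 1 − 0.95^2 = 9.8% |
| 3 | 1 − 0.95^6 = 26.5% | 1 − 0.95^3 = 14.3% |
| 4 | 1 − 0.95^8 = 33.7% | 1 − 0.95^4 = 18.5% |
| 5 | 1 − 0.95^10 = 40.1% | 1 − 0.95^5 = 22.6% |
| 6 | 1 − 0.95^12 = 46.0% | 1 − 0.95^6 = 26.5% |

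By arm, the risk first passes 50% at k = 7 (1 − 0.95^14 = 51.2%). The sample size does not enter the formula.

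Independence overstates the risk somewhat. A simulation with medication use correlated at 0.5 (10,000 runs, 32 per arm, tests by arm) gives 23.5% for k = 3 and 33.8% for k = 5.

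**2. What a single arm can detect.** The critical |r| is t / √(n − 2 + t²). With n = 32 and t = 2.042 on 30 df, it is 2.042 / √(30 + 4.170) = 0.349.

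**3. Significance in exactly one arm when the true r is the same in both.** Power p per arm comes from Fisher's z: the mean of the test statistic is atanh(r) × √29, compared with ±1.96. The probability wanted is 2p(1 − p).

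| true r in both arms | p | exactly one arm significant |
|---|---|---|
| 0 | 0.050 | 9.5% |
| 0.2 | 0.194 | 31% |
| 0.3 | 0.385 | 47% |
| 0.4 | 0.626 | 47% |
| 0.5 | 0.841 | 27% |

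The maximum of 2p(1 − p) is 50%, reached near r = 0.35.

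**4. An example.** Take r = 0.40 in one arm (p = 0.023) and r = 0.20 in the other (p = 0.27). The direct comparison is (atanh 0.40 − atanh 0.20) / √(2/29) = (0.424 − 0.203) / 0.263 = 0.84, so p = 0.40. One arm is significant and the other is not, yet there is no evidence that they differ.

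**5. The t-test.** For a yes/no variable, the Pearson test and the equal-variance t-test are the same test. A numerical check (12 users, 20 non-users) gave p = 0.2117 from both.

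**The case against.** The strongest reply is that this is one secondary sentence. The stated purpose is gastrointestinal activation, the efficacy conclusion is tied to the data described before this sentence, and no decision rule hangs on the medication analysis. That stands, and it limits the consequence.

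Four stronger readings are tempting, and the documents do not support them.

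- **That chance findings are likely.** The number of types is not stated, and up to six types by arm the risk is below one half.
- **That small arms cause the false positives.** They do not; the number of tests does. Small arms lower power and make the two arms disagree more often, which is a separate problem.
- **That a one-arm result would be misread.** The plan describes no comparison of correlations between arms and no rule for reading a one-arm result. It could be misread, no more. Under the pooled reading the question does not arise.
- **That medication types are given together.** The document does not say so. If they are, the independence figures are somewhat high and the separate estimates in a joint model are less precise.

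The 47% is also close to the ceiling of 50%, so it should be read with the 31% and 9.5% beside it.

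It can fairly be said that part of the gap is missing detail. But the method that is stated, separate correlations backed by a t-test, is itself weaker than one model on the same data.

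**Conclusion.** The concern holds in a limited form. The stated method tests several medication types one at a time, with no control of the overall error and no means of saying whether the arms differ. For any k of 2 or more, the chance of a spurious association is above 5%: roughly two to nine times that level over k = 2 to 6 for both groupings (9.8% / 5% to 46.0% / 5%). If the analysis is by arm, discordant arms are a common outcome under a shared moderate correlation. The t-test is no safeguard where use is coded yes/no; for other codings the plan does not say how the groups would be formed.

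These sizes rest on assumed values for the number of types and the significance level, on independent tests, and on arms of 32. The bowel-function efficacy comparison is not directly affected. This is worth correcting, but it does not threaten the main result.

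**What to change.** Replace the separate correlations and the confirming t-test with one linear regression of length of stay on arm plus all medication types, in all 64 women. List the types and their coding. Test the medication terms together with one joint F-test, and report each estimate with its 95% confidence interval.

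Make no statement about one arm alone unless the arm-by-medication terms, one per type, have been tested jointly. Label the analysis exploratory and associational. Do not read the arm coefficient in this model as a treatment effect, because medication use is recorded after randomisation.

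The cost is one regression in the same software, on data already collected, and a few lines of SAP text. As the text is in the past tense, the same model can be run as a re-analysis.

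The downside is precision. With k = 6, the model with interactions has 1 + 1 + 6 + 6 = 14 coefficients for 64 women. Even for a single type, comparing correlations between two arms of 32 needs a Fisher-z difference of (1.96 + 0.84) × 0.263 = 0.74 for 80% power, for example r = 0.63 against 0. Individual medication and interaction estimates will be imprecise, more so if types are used together, and the report should say so.
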